**UX001-CL302 Amendment 1**

**17 June 2016**

---

The original protocol of UX001-CL302 (dated 10 Feb 2016) has been modified by Amendment 1 to incorporate a number of changes based on additional information acquired since the beginning of the study. The major changes to the protocol impacting the conduct of the study are summarized below. Additional changes have also been made to provide supportive background information and rationale for the proposed changes (along with minor edits for consistency and clarity) but are not detailed in this summary.

1. The protocol was amended to allow for the inclusion of subjects who complete the UX001-CL202 study. This change affected multiple sections of the protocol, including the synopsis, [Table 2.1](#), and Inclusion Criterion 1 (Section [7.3.1](#)). Subjects enrolling from the UX001-CL202 study will follow the same schedule of events as subjects who roll over from the UX001-CL301 study.

*Rationale: This change was made to provide subjects in UX001-CL202 an opportunity to continue treatment with Ace-ER (6 g/day) and obtain long-term safety and efficacy data in UX001-CL302.*

2. With regard to Change #1 above, the amendment clarifies that subjects who rollover from UX001-CL202 will receive 6 g/day of Ace-ER. No subjects will receive 12 g/day in this study.

*Rationale: Evaluations of Ace-ER in patients with GNEM have shown that the 6 g/day is the optimal dose. Clinical efficacy with 6 g/day surpassed the 3 g/day dose and 12 g/day did not appear to confer additional benefit beyond that observed with 6 g/day, with an increase in GI disturbance, most notably flatulence.*

3. Treatment duration language changed to remove “until commercial availability of study drug in subject’s region.” This change affected multiple sections of the protocol, including Synopsis, [Figure 2.1](#) and Section [7](#). The treatment duration on the study will be 24 Months.

*Rationale: This change was made to incorporate feedback from MHRA in order to clarify end of study.*

4. [Table 7.5.5.1](#) was updated to include blood/RBC and leukocyte esterase to the urinalysis panel and to add a footnote indicating that microscopic evaluation will be conducted for abnormal urine test results.

*Rationale: The change was made to clarify the analytes that will be tested in urinalysis and confirm that microscopic evaluation will be conducted for abnormal test results.*

5. Language was added to the synopsis and multiple sections of the protocol instructing that for UX001-CL202 subjects, assessments that cannot be safely performed due to disease progression should not be administered.

*Rationale: This added text will ensure the safety of subjects who rollover from the UX001-CL202 study and are unable to perform an assessment due to disease progression.*

6. The number of samples drawn from each subject ([Table 7.5.5.1.1](#)) was increased for the serum sialic acid assessments from 2 samples to 5 samples. The total volume of blood sample to be obtained increased from 87 mL to 108 mL for subjects rolling over from UX001-CL203 and from 108 to 129.5 for subjects rolling over from UX001-CL301.

*Rationale: The change was made to clarify the total blood volume required to ensure a primary and back-up serum sialic acid sample are obtained and also to clarify the total volume of blood to be obtained during the study.*

7. Record Retention: Section [8.4.3](#) has been updated to state that all study records must be retained for at least 25 years after the end of the clinical trial or in accordance with national law.

*Rationale: This administrative change has been made to reflect upcoming changes to EU clinical trial regulations and current regulations by other health authorities.*

## 2 SYNOPSIS

**TITLE OF STUDY:**

A Phase 3b Open-label Extension Study to Evaluate the Safety and Efficacy of Aceneuramic Acid Extended-Release (Ace-ER) Tablets in Patients with GNE Myopathy (GNEM) or Hereditary Inclusion Body Myopathy (HIBM)

**PROTOCOL NUMBER:**

UX001-CL302

**STUDY SITES:**

Approximately 15 sites, globally

**PHASE OF DEVELOPMENT:**

Phase 3b

**RATIONALE:**

GNEM (or HIBM), is a severe, progressive myopathy caused by a defect in the biosynthetic pathway for sialic acid (SA). Substrate replacement is a potential therapeutic strategy based on the success of replacing missing SA and reducing muscle disease in a relevant mouse model of the human disease. Successful use of SA replacement therapy in humans is believed to depend upon providing steady, long-term exposure to the compound in an extended-release form (such as Ace-ER), given SA's short half-life. A Phase 2, placebo-controlled study evaluating Ace-ER at 2 doses for 48 weeks (UX001-CL201) found that the higher dose of 6 g/day Ace-ER stabilized a composite of upper extremity muscle strength (UEC score) compared with placebo or the lower 3 g/day dose; this finding was supported by improvements in functional outcome on the GNE Myopathy Functional Activities Scale (GNEM-FAS). This Phase 3b extension study will assess the long-term safety of Ace-ER in patients who participated in and completed the UX001-CL202, UX001-CL301, or UX001-CL203 studies; in addition, efficacy of 6 g/day Ace-ER will be further evaluated in GNEM patients, including those able to walk  $\geq 200$  m in the 6-minute walk test (6MWT) (roll over subjects from UX001-CL301 and naïve subjects from UX001-CL202) and GNEM patients with severe ambulatory impairment (roll over subjects from UX001-CL203).

**OBJECTIVE:**

- To evaluate the long-term safety and efficacy of Ace-ER treatment of GNE Myopathy subjects

**ENDPOINTS:**

**Overall Safety Endpoint (Primary Endpoint):** Evaluate the long-term safety of 6 g/day Ace-ER treatment in subjects with GNE Myopathy

**Overall Efficacy Endpoints:** Evaluate the long-term effect of 6 g/day of Ace-ER treatment in subjects with GNEM. Efficacy will be evaluated as follows:

**For Subjects Enrolling from UX001-CL202 and UX001-CL301:**

- Muscle strength as measured by dynamometry
- Mobility, strength, and function using a series of physical performance measures
- Functional disability using an patient- and clinician-reported questionnaire

**For Subjects Enrolling from UX001-CL203:**

- Change in GNEM-FAS Expanded Version total score and mobility, upper extremity and self-care domain scores
- Change in upper extremity strength in grip, key pinch, shoulder abductors and wrist extensors and in lower extremity muscle strength in the knee extensors as measured by dynamometry
- Evaluate the effect on 6g/day Ace-ER on health-related quality of life (HRQoL), patient reported outcomes (PRO), and biomarkers of sialylation

**STUDY DESIGN AND METHODOLOGY:**

This open-label extension study of Ace-ER will assess the long-term safety and efficacy of Ace-ER treatment over a period of 24 months. Approximately 165 subjects from the UX001-CL202, UX001-CL301, and UX001-CL203 studies will be eligible to enroll in the study.

[figure not shown]
Subjects will take 4 tablets (500 mg Ace-ER each for 2 g per dose) orally 3 times per day (TID). The dose should be taken with food (i.e. within 30 minutes after a meal or snack). Subjects being treated with 12 g/day Ace-ER in UX001-CL202 will be transitioned to the 6 g/day Ace-ER dose in this protocol. Treatment will be administered for a total of 24 months. Study visits will occur every 8 weeks for 24 weeks and then every 6 months for subjects enrolling from UX001-CL202 or UX001-CL301. For subjects enrolling from the UX001-CL203 study, study visits will occur every 6 months. Assessments will be performed as outlined in the Schedule of Events ([Table 2.1](#)).

Safety will be evaluated by review of the incidence and frequency of AEs and SAEs and clinically significant changes in interval history, physical examination results, vital signs, clinical laboratory test results, the Columbia Suicide Severity Rating Scale (C-SSRS), and concomitant medications.

Blood samples will be collected to evaluate biomarkers (for example sialylation of serum proteins before and after treatment) to determine their utility in predicting clinical outcomes.

Efficacy will be evaluated based on assessments used in the parent study from which subjects roll over (subjects enrolling from UX001-CL202 will follow the same schedule of events as subjects who roll over from UX001-CL301), and include dynamometry as a measure of muscle strength and patient- and clinician-reported outcome measures as indicators of physical functioning and quality of life. Figure 2.1 provides a schematic of the study design.

**Figure 2.1: Study Schema**

**NUMBER OF SUBJECTS PLANNED:**

Approximately 165 adult subjects with GNEM are expected to roll-over from the UX001-CL202, UX001-CL301 or UX001-CL203 studies to participate in this extension study.

**DIAGNOSIS AND CRITERIA FOR INCLUSION AND EXCLUSION:**

Individuals eligible to participate in this study must meet all of the following criteria:

1. Have completed the UX001-CL202, UX001-CL301, or UX001-CL203 studies
2. Willing and able to provide written, signed informed consent after the nature of the study has been explained, and before any research-related procedures are conducted
3. Willing to comply with all study procedures
4. Female participants of child-bearing potential or male participants with female partners of child-bearing potential who have not undergone a bilateral salpingo-oophorectomy and are sexually active must consent to use a highly effective method of contraception as determined by the site investigator (i.e., oral hormonal contraceptives, patch hormonal contraceptives, vaginal ring, intrauterine device, physical double-barrier methods, surgical hysterectomy, vasectomy, tubal ligation or true abstinence [when this is in line with the preferred and usual lifestyle of the subject], which means not having sex because the subject chooses not to), from the period following the signing of the informed consent through 30 days after last dose of study drug
5. Females of childbearing potential must have a negative pregnancy test at Screening and be willing to have additional pregnancy tests during the study. Females considered not of childbearing potential include those who have been in menopause for at least two years, have had tubal ligation at least one year prior to Screening, or who have had a total hysterectomy or bilateral salpingo-oophorectomy

Individuals who meet any of the following exclusion criteria will not be eligible to participate in the study:

1. Ingestion of N-acetyl-D-mannosamine (ManNAc) or related metabolites; intravenous immunoglobulin (IVIG); or anything that can be metabolized to produce SA in the body within 60 days prior to the Screening Visit
2. Has had any hypersensitivity to SA or its excipients that, in the judgment of the investigator, places the subject at increased risk for adverse effects
3. Pregnant or breastfeeding at Screening or planning to become pregnant (self or partner) at any time during the study
4. Use of any investigational product (except for Ace-ER/SA-ER as part of the parent study) or investigational medical device within 30 days prior to Screening, or anticipated requirement for any investigational agent prior to completion of all scheduled study assessments
5. Has a condition of such severity and acuity, in the opinion of the investigator, that it warrants immediate surgical intervention or other treatment or may not allow safe participation in the study
6. Has a concurrent disease, active suicidal ideation, or other condition that, in the view of the investigator, places the subject at high risk of poor treatment compliance or of not completing the study, or would interfere with study participation or would affect safety

**INVESTIGATIONAL PRODUCT, DOSE, AND MODE OF ADMINISTRATION:**

Each Ace-ER tablet contains 500 mg of SA in an extended release formulation for a total weight of 1200 mg/tablet. The drug will be administered by the oral route and will be divided into a TID regimen: 4 tablets taken in the morning, early evening, and before bedtime (qHS). The dose should be taken with food (i.e., within 30 minutes after a meal or snack).

**REFERENCE THERAPY, DOSE, AND MODE OF ADMINISTRATION:**

Not applicable

**DURATION OF TREATMENT:**

The total treatment duration will be 24 months. A Safety Follow-up visit will be conducted by phone 30 days (+5 days) after last dose of study drug.

**CRITERIA FOR EVALUATION:****Safety:**

Safety will be evaluated by the incidence frequency, and severity of AEs and SAEs, and clinically significant changes from baseline to scheduled time points in the following:

- Interval history
- Vital signs
- Physical examination results
- Clinical laboratory results
- C-SSRS (a measure of suicidal ideation and behavior)
- Concomitant medications

**Drug Concentration Measurements:**

Serum Free Sialic Acid: The change in free SA level in serum (trough) will reflect the absorption of SA during treatment.

Urine Sialic Acid - Free, Total and Bound: The urine SA level (corrected for creatinine) will reflect the absorption of SA and the incorporation into sialylated proteins and oligosaccharides during treatment.

Urine Testing for ManNAc: Urine will be tested for the presence of ManNAc to detect compliance with prohibited medication restrictions.

**Efficacy:**

Efficacy evaluations will be based on the parent study (UX001-CL202, UX001-CL301, or UX001-CL203) from which the subjects enroll. Subjects enrolling from UX001-CL202 will follow the same schedule of events as subjects who roll over from UX001-CL301. For UX001-CL202 subjects, assessments that cannot be safely performed by a subject due to disease progression should not be administered.

**UX001-CL301 and UX001-CL202:** For subjects enrolling from these studies, efficacy will be evaluated by changes in upper and lower extremity muscle strength and function, and self-reported physical functioning. Results from baseline assessments in this study will be compared with those of post-treatment assessments listed in the Schedule of Events ([Table 2.1](#)), with efficacy conclusions

based on change from baseline over the treatment period.

Primary Clinical Efficacy Variable :

**Upper Extremity Composite Score:** Muscle strength based on the maximum voluntary isometric contraction (MVIC) against a dynamometer will be measured bilaterally in the following upper extremity muscle groups: gross grip, shoulder abductors, elbow flexors, and elbow extensors.

The UEC is derived from the sum of the average of the right and left total force values (measured in kg).

Secondary Clinical Efficacy Variables:

- **GNEM Functional Activities Scale:** Physical functioning will be assessed using a disease-specific measure. Scores on the mobility domain and the upper extremity domain of the GNEM-FAS will be analyzed separately as secondary variables.
- **Lower Extremity Composite (LEC) Score:** Muscle strength based on MVIC against a dynamometer will be measured bilaterally in the following lower extremity muscle groups: knee flexors, hip flexors, hip extensors, hip abductors and hip adductors. The LEC is derived from the sum of the average of the right and left total values (measured in kg).
- **Number of Stands in the Sit-to-Stand Test:** Lower extremity function will be assessed using a sit-to-stand test. The number of times the subject can rise from a seated to a standing position in a 30-second period will be recorded.
- **Number of Lifts in the 30-second Weighted Arm Lift Test:** Upper extremity function will be assessed using a weighted arm lift test performed bilaterally. The number of times the subject can raise a 1 kg weight above the head in a 30-second period will be recorded.
- **Total Force (kg) and Percent Predicted Force in the Knee Extensors:** Bilateral total force will be reported. The percent predicted total force value will be determined based on reference equations adjusting for age, gender, height, and weight.
- **Meters Walked in the Six-Minute Walk Test:** The total distance walked (meters) in a six minute period will be measured as well as the percent predicted distance based on normative data for age and gender.

Tertiary Efficacy Variables:

- **Upper Extremity Composite and Lower Extremity Composite Percent Predicted:** The percent predicted total force values will be determined based on reference equations adjusting for age, gender, height, and weight. The percent predicted force will be calculated for each side and the bilateral percent predicted values will be averaged for each upper extremity muscle group. The mean of the four averages in percent predicted scores will be calculated to create a percent predicted UEC score, and analyzed relative to baseline to create a UEC mean change in percent predicted score. Similar methodology will be used to determine the percent predicted total force values for the LEC.
- **Total Force (kg) and Percent Predicted in Each Individual Muscle Group:** Bilateral total force and percent predicted total force for each individual muscle group included in the UEC and LEC will be reported.
- **Total Score on the GNEM-FAS**
- **Self-Care Domain Score on the GNEM-FAS**
- **Score on the Individualized Neuromuscular Quality of Life Questionnaire:** The scores on a 45-

item self-report questionnaire on the impact of key muscle disease symptoms on the ability to perform basic activities of daily living, functional independence, relationships and overall well-being will be recorded.

- Creatine Kinase Levels: CK levels in serum will be measured to assess the degree of reduction of CK levels observed as a surrogate for muscle injury.

**UX001-CL203:** Efficacy will be evaluated by changes in upper and lower extremity muscle strength, self-reported physical functioning, and health related quality of life outcome measures. Results from baseline assessments will be compared with those of post-treatment assessments listed in the Schedule of Events ([Table 2.1](#)), with efficacy conclusions based on change from baseline over the treatment period.

Clinical Efficacy Variables:

- GNEM-FAS – Expanded Version: Physical functioning will be assessed using a disease-specific, self-reported outcome measure. Scores on the mobility, self-care and upper extremity domains of the GNEM-FAS Expanded Version will be analyzed separately as secondary variables
- Upper Extremity Muscle Strength: Muscle strength measured as the maximum voluntary isometric contraction (MVIC) against a dynamometer will be measured bilaterally in the following upper extremity muscle groups: grip, key pinch, shoulder abductors and wrist extensors. A UEC, will be derived as the sum of the average of the right and left total force values (measured in kg) when force values are available for all muscle groups tested
- Lower Extremity Muscle Strength: Muscle strength based on the maximum voluntary isometric contraction (MVIC) against a dynamometer will be measured bilaterally for the knee extensors in subjects that can be positioned for testing.

Exploratory Variables:

- Short Form Health Survey-36 (SF-36): Quality of life will be assessed using the SF-36 with scores reported for the Physical Component Summary, Mental Component Summary and the eight subscales, including physical functioning, role-physical, bodily pain, general health, social functioning, role-emotional, vitality, and mental health
- Biomarkers: Serum will be obtained at all study visits to evaluate CK, serum aceneuramic acid, and potential biomarkers of sialylation and other markers of muscle injury and remodeling

## STATISTICAL METHODS:

### **Sample Size:**

Approximately 165 adult subjects with GNEM are expected to roll-over from UX001-CL202 (N=55), UX001-CL301 (N=80), and UX001-CL203 (N=30) studies to participate in this extension study.

### Efficacy Analyses:

Separate analyses will be performed for subjects enrolling from each parent study.

The full analysis set will include all subjects with a baseline measurement and at least one post-baseline measurement. This set will be used for the analyses of all efficacy endpoints.

Baseline values for each endpoint will be defined as the last scheduled data collection visit before first dose according to the Schedule of Events ([Table 2.1](#)).

Efficacy analyses will use generalized estimating equation (GEE) to evaluate trends over time with respect the changes from baseline for the primary variables, and all secondary and tertiary efficacy variables. Baseline will be included as a covariate in the model. This method will be the primary analysis method for all repeated measures endpoints.

The statistical analyses will be reported using summary tables, figures, and data listings. Statistical tests will be 2-sided at the alpha=0.05 significance level. Continuous variables will be summarized with means, standard deviations, medians, minimums, and maximums. Categorical variables will be summarized by counts and by percentages of subjects in corresponding categories.

### Safety Analyses:

Safety will be evaluated for the overall study population as well as for subjects from the UX001-CL202, UX001-CL301, and UX001-CL203 studies. The safety analysis set consists of all subjects who receive at least one dose of study drug. Safety will be evaluated by the incidence, frequency, and severity of AEs and SAEs, and clinically significant changes from study baseline to scheduled time points in: interval history, vital signs, physical examination findings, clinical laboratory evaluations, C-SSRS, and concomitant medications

All AEs will be coded using the Medical Dictionary for Regulatory Activities (MedDRA). The incidence and frequency of AEs will be summarized by System Organ Class (SOC), Preferred Term (PT), severity, and relationship to treatment. The numbers (frequency) and incidence rates of AEs and SAEs will be summarized by treatment group. A by-subject listing will be provided for those subjects who experience a serious adverse event (SAE), including death, or experience an adverse event (AE) associated with early withdrawal from the study or study drug treatment.

Clinical laboratory data will be summarized by the type of laboratory test. The frequency and percentage of subjects who experience abnormal clinical laboratory results (i.e. outside of reference ranges) and/or clinically significant abnormalities will be presented for each clinical laboratory measurement.

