##### **7.4.6.2 Permitted Medications**

Other than medications specifically prohibited in this study, subjects may receive concomitant medications as required. Medications (prescription, over-the-counter, and herbal) and nutritional supplements taken during the 30 days prior to Screening will be reviewed and recorded at the Screening visit. At the Baseline visit, current medications will be recorded. At each visit, any concomitant medications added or discontinued during the study should be recorded on the CRF.

The site personnel should record the following in the CRF: date and time the medication was taken, the name of the medication, and the reason the medication was taken.

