#### **7.6.6 Safety Analyses**

Safety will be evaluated for the overall study population as well as for subjects from the UX001-CL202, UX001-CL301, and UX001-CL203 study.

The safety analysis set will be used for the analyses of all safety endpoints. Safety will be evaluated by the incidence, frequency and severity of AEs and SAEs, and clinically significant changes from study baseline to scheduled time points in:

- Interval history
- Vital signs
- Physical examination findings
- Clinical laboratory evaluations
- Suicidal ideation and behavior assessments (C-SSRS)
- Concomitant medications

All AEs will be coded using the Medical Dictionary for Regulatory Activities (MedDRA). The incidence and frequency of AEs will be summarized by System Organ Class (SOC), Preferred Term (PT), severity, and relationship to treatment. The numbers (frequency) and incidence rates of AEs and SAEs will be summarized by treatment group. A by-subject listing will be provided for those subjects who experience a SAE, including death, or experience an AE associated with early withdrawal from the study or study drug treatment.

Clinical laboratory data will be summarized by the type of laboratory test. The frequency and percentage of subjects who experience abnormal clinical laboratory results (i.e. outside of reference ranges) and/or clinically significant abnormalities will be presented for each clinical laboratory measurement. For each clinical laboratory measurement, descriptive statistics will be provided for study baseline and all subsequent post-treatment scheduled visits. Changes from study baseline to the post-treatment visits will also be provided.

Changes in findings from study baseline physical examinations will be tabulated for each subject by examination category. If there are examination findings that change in more than one subject, these will be tabulated in a separate table and expressed as the number of subjects with the change out of the total. No statistics will be applied to the physical examination findings.

The SAP will provide additional details on the planned safety analyses.

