4.1.2 Other Safety Endpoints

Other safety endpoints include clinically significant changes from baseline to scheduled time points in the following:

- Interval History
- Vital signs
- Physical examination results
- Clinical laboratory results
- C-SSRS (a measure of suicidal ideation and behavior)
- Concomitant medications

Drug concentration endpoints will be evaluated for the following:

- Changes from baseline in free SA level in serum;
- Changes from baseline in urine SA level;
- Frequency and percentage of subjects with the presence of ManNac detected from urine testing.

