5 DEFINITIONS

5.1 Baseline

Two baselines are defined for the statistical analysis variable derivations.

- **Current study baseline** is defined as the last observed value before the first dosing of the study drug for CL302.
- **Parent study baseline** is defined as the last observed value before the first dosing of the IP study drug from CL202, CL203, or CL301 depending on which study the subject was enrolled from.

Current study baseline is defined for all safety summaries and analyses.

Efficacy summaries and analyses will be performed upon the parent study baseline and the current study baseline as specified in [Table 8.1.1](#).

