8.7.2 Concomitant Medication

The number and percent of concomitant medications in CL302 will be summarized by ATC class and preferred term (per WHO-drug dictionary) in the safety analysis set.

If a subject took a specific medication multiple times or took multiple medications within a specific therapeutic class, that subject will be counted only once for the coded drug name or therapeutic class.

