8.7.7 Suicidal Ideation

The Columbia Suicide Severity Rating Scale (C-SSRS) is a standardized rating instrument used to assess the suicidal ideation and behavior in an at-risk population and will be administered at each visit. Any 'Yes' response from C-SSRS will be listed.

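### Concomitant medications and C-SSRS are defined as change from the CL302 baseline, but the SAP summarises no change: carried-in and newly started drugs share one count, and C-SSRS 'Yes' answers are listed without a count

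*Protocol*

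**What the plan says.** The definition is consistent across the documents. The protocol synopsis (Safety Analyses) lists "clinically significant changes from study baseline to scheduled time points in: interval history, vital signs, physical examination findings, clinical laboratory evaluations, C-SSRS, and concomitant medications". The synopsis criteria for evaluation speak of "clinically significant changes from baseline to scheduled time points in the following", and protocol 7.6.6 of "clinically significant changes from study baseline to scheduled time points in". SAP 4.1.2 agrees: "Other safety endpoints include clinically significant changes from baseline to scheduled time points in the following", with C-SSRS and concomitant medications both in its list. SAP 5.1 settles which baseline applies: "Current study baseline is defined for all safety summaries and analyses".

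The planned outputs are narrower:

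- **Concomitant medications (SAP 8.7.2).** "The number and percent of concomitant medications in CL302 will be summarized by ATC class and preferred term". A subject counts once per coded drug or therapeutic class, however often it was used. The section mentions no baseline, visit or start date.
- **C-SSRS (SAP 8.7.7).** The only output is that any 'Yes' "response from C-SSRS will be listed".

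The data needed to show change are collected. Protocol 7.4.6.2 says that "any concomitant medications added or discontinued during the study should be recorded on the CRF". Protocol 7.5.5.8 asks for medication changes at each visit. SAP 7.2.3 completes partial medication dates by reference to the first dose in this study. Table 2.1, note d, specifies a Baseline C-SSRS form followed by Since Last Visit forms.

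**The concern.** An endpoint defined as a change needs an output that displays the change. The medication table appears to put a drug the subject brought into CL302 in the same cell as a drug first needed during CL302. A class with many new starters could then look the same as a class with none.

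This matters because safety is the primary objective and the sponsor already treats supportive medication as relevant to a signal. Protocol 5.2.4 reports more gastrointestinal disturbance on Ace-ER than on placebo in the first 24 weeks of the earlier controlled study. The monitored gastrointestinal terms in SAP Appendix 10.6.1 include antacid, antidiarrhoeal and laxative therapy. New starts of such drugs would be useful corroboration, above all in subjects who took placebo in CL301 and receive Ace-ER in CL302.

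For C-SSRS, a listing leaves the reader to count subjects and find a denominator, although SAP 8.1 says that categorical variables are summarised by number and percentage.

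**Working it through.** No sample size, power or event figure in the documents bears on this point. The check sets definitions beside outputs and adds two small illustrations.

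**1. Definition against output within the SAP**

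| Item | Planned output | Is change summarised? |
|---|---|---|
| Laboratory values (8.7.3) | Values and change from CL302 baseline by visit | Yes |
| Vital signs (8.7.4) | Values and change from CL302 baseline by visit | Yes |
| Interval history (8.7.6) | Subjects reporting change since last visit | Yes, visit to visit |
| Adverse events (8.7.1) | Treatment-emergent rule; carried-over events excluded unless worsened | Yes |
| Concomitant medications (8.7.2) | Subjects by class and drug in CL302 | No |
| C-SSRS (8.7.7) | Listing of any 'Yes' | Not counted; may be visible per subject |

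SAP section 1 gives the SAP precedence on analysis methods, so the protocol wording does not fill the gap.

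**2. Can the medication table register a change?** Assume that 'in CL302' covers any use during the study, and take the protocol's planned N = 165.

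- Case A: 40 subjects take a drug at baseline and continue it. Printed: 40/165 = 24.2%.
- Case B: nobody takes it at baseline and 40 start it after first dose. Printed: 40/165 = 24.2%.

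With the SAP's planned 180 subjects, both cases print 40/180 = 22.2%. The 40 is assumed; the equality holds for any count.

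**3. Mixed case.** Let b be the share on a drug class at entry and s the share of the others who start it on study. The printed share is b + (1 − b) × s. With b = 0.40 (assumed):

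- s = 0: 0.40
- s = 0.05: 0.40 + 0.60 × 0.05 = 0.43
- s = 0.10: 0.40 + 0.60 × 0.10 = 0.46
- s = 0.20: 0.40 + 0.60 × 0.20 = 0.52

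Because b is not shown, a printed 46% could mean 6 points of new use (b = 0.40, s = 0.10) or none (b = 0.46, s = 0).

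**4. C-SSRS.** If the listing carries subject and visit (the SAP does not specify its columns), a subject with no 'Yes' on the Baseline form and a 'Yes' at Week 24 is distinguishable from one with 'Yes' at both. Change can be read per subject but is never totalled.

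**5. What the CL302 baseline means.** Protocol 7.6.1 expects 55 subjects from CL202 and 30 from CL203, both open-label Ace-ER studies: 85/165 = 51.5%. Former active-arm CL301 subjects add to this; the documents do not give their number. For more than half of the planned population, a drug started after first CL302 dose is not a drug started after first Ace-ER exposure.

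**The case against.** The strongest reply is that the documents already have a route for clinically significant medication change. Protocol 7.5.5.9 directs that such changes be recorded as AEs or SAEs where appropriate. AEs starting on or after first dose are tabulated as treatment-emergent, and SAP 8.7.1.1 with Appendix 10.6.1 adds incidence tables that include supportive gastrointestinal therapy terms. Clinical significance needs judgement, and this route supplies it. It follows that newly needed gastrointestinal medication would not simply go unseen. But the route is partial: it depends on an open-label decision on what is appropriate, does not name C-SSRS, and does not yield the medication summary that SAP 4.1.2 defines.

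A reader might infer that neither output can show a change. For C-SSRS the documents do not support that. Each later form covers the period since the previous visit, so a listed post-baseline 'Yes' is informative by itself. SAP 8.2 reports the safety set by parent study and total, so a denominator could be found. What is missing is only the count.

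A reader might also infer that the primary safety result is compromised. It is not: SAP 4.1.1 makes the primary endpoint AEs and SAEs assessed as related to Ace-ER.

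Two further objections stand as limits. SAP 8.7.2 does not define use in CL302, so pooling is the natural reading and not stated text. And a new-start table has no concurrent control and, for most subjects, begins from an on-drug baseline, so it cannot be read as the effect of starting Ace-ER.

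**Conclusion.** The point holds, with modest importance. Both documents define concomitant medications and C-SSRS as clinically significant change from baseline, and the SAP plans no summary of change for either.

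The medication part is the firmer one. If SAP 8.7.2 covers any use on study, its table cannot separate drugs ongoing at first CL302 dose from drugs started later, whatever the numbers. The illustrated shares (24.2% in both cases; 40% to 52% in the mixed case) rest on assumed counts and show the mechanism, not an expected size.

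The C-SSRS part is minor: the listing can reveal a new 'Yes', but without a count or denominator.

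These are among the other safety endpoints of SAP 4.1.2, safety reporting is descriptive, and no test depends on them. The change is worth making because it is cheap and brings the outputs into line with the SAP's own definition.

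**What to change.** **SAP 8.7.2.** Tabulate by parent study (CL301 by former arm and combined) and overall:

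- (a) medications ongoing at first CL302 dose;
- (b) medications started on or after first CL302 dose.

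Name (b) as the change summary for this endpoint. Use the date rules of SAP 7.2.3, with one addition. Those rules move a partial start date in the month or year of first dose to the first-dose date, and leave a date with unknown year missing. State that a medication recorded as current at the Baseline visit goes in (a) in either situation.

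Add a note that for CL202, CL203 and former active-arm CL301 subjects, (b) means change since the CL302 baseline and not since first Ace-ER exposure. Former CL301 placebo subjects are the most informative group.

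**SAP 8.7.7 (minor).** Keep the listing, showing visit and form. Add n/N of subjects with any Since Last Visit 'Yes' after first dose, separately for ideation and behaviour, and the subset with no such 'Yes' on the Baseline form.

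If the sponsor prefers not to add tables, SAP 4.1.2 should at least be reworded to match the outputs. That removes the inconsistency but leaves change unsummarised.

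**Cost.** SAP wording and a few extra programmed tables. No new data are needed.
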